6.3. Handling of Dropouts or Missing Data

The missing data strategy has been described in the H0P-MC-CPMP SAP Version 4.

In addition, to use of Bayesian MMRM model described in the H0P-MC-CPMP SAP, to examine the effect of missing data, constrained cell means MMRM with multiple imputations will be applied as a sensitivity analysis to assess change from baseline to postbaseline measure for visual analog scale (VAS) and NRS.

For these continuous efficacy endpoints, a Markov chain Monte Carlo method will be used to impute intermittent (non-monotone) missing visit data and a set of Bayesian regressions will be used for the imputation of monotone dropouts. The variable pooled investigative site, treatment, age, gender, baseline pain severity categories will be included for imputing non-monotone missingness, and primary adverse events (AEs) leading to treatment discontinuation can be included as an additional variable for imputing monotone missingness. Subject-level indicator of primary AEs leading to treatment discontinuation is set 1 for patients experiencing AEs in preferred terms (PT), including nausea, dizziness, fatigue, abdominal discomfort, abdominal pain lower, abdominal pain upper, constipation, lethargy, somnolence, at any time during double-blinded (DB) treatment period; 0 otherwise. The number of imputed data sets will be 200 and the initial seed for imputing intermittent missing data is 12345 and for imputing monotone missing

data is 678910. Within the program, the seed will be used to generate 200 seeds needed for imputation.

The analysis model will utilize the constrained cell means MMRM so that a common mean is estimated at the baseline for each imputed dataset. The pooled investigative site, treatment and time interaction, baseline pain severity categories will be included as fixed effects. Results across the imputed datasets will be aggregated using SAS procedure MIANALYZE in order to compute LSmeans and standard errors for the treatment comparisons.

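### The multiple-imputation sensitivity analysis in SAP 6.3 assumes missing at random, so with about 33% dropout no visible analysis tests whether dropouts would have done worse than that assumption predicts

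*SAP*

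**What the plan says.** SAP 6.3 first defers to the master plan: "The missing data strategy has been described in the H0P-MC-CPMP SAP Version 4". It then adds an analysis of its own for VAS and NRS: "to examine the effect of missing data, constrained cell means MMRM with multiple imputations will be applied as a sensitivity analysis".

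- **Imputation method.** Intermittent gaps are filled by Markov chain Monte Carlo. For the rest, "a set of Bayesian regressions will be used for the imputation of monotone dropouts". There are 200 imputed data sets.
- **Imputation variables.** "The variable pooled investigative site, treatment, age, gender, baseline pain severity categories will be included for imputing non-monotone missingness". For dropout, "primary adverse events (AEs) leading to treatment discontinuation can be included as an additional variable for imputing monotone missingness". That indicator is set to 1 for a list of preferred terms occurring "at any time during double-blinded (DB) treatment period; 0 otherwise".
- **Analysis model.** "The pooled investigative site, treatment and time interaction, baseline pain severity categories will be included as fixed effects". Results are pooled "in order to compute LSmeans and standard errors for the treatment comparisons".

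Elsewhere, SAP 6.1 sets a hypothetical estimand: the outcome had participants stayed on their randomised treatment. SAP 6.2 makes the painDETECT category (at least 19, or below 19) the randomisation stratification factor. It assigns that factor to the primary, secondary and some exploratory models. SAP 6.16 adds a frequentist MMRM as a sensitivity analysis. SAP 5.2 and Protocol 1.1 and 9.2 plan for at most 200 randomised and about 33% dropout.

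**The concern.** The hypothetical estimand asks for values that are never observed in participants who stop. MAR is a natural main assumption for it and is not challenged here, but the trial's data cannot verify it. A sensitivity analysis meant to show the effect of missing data is most useful if it varies that assumption.

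Section 6.3 never uses the term MAR. It follows from the method: each missing value is drawn from a regression on observed data and randomised arm, and nothing is added to the draw. The MMRM in 6.16 relies on the same assumption through its likelihood. Comparing the two can show sensitivity to the conditioning set or to implementation. It cannot show what happens if dropouts differ from what their observed data predict. Agreement between the two would then say nothing on this point to those making the proof-of-concept decision.

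A smaller matter is that both covariate lists in 6.3 leave out painDETECT. The RMDQ model in 6.10.3 has the same three effects as the 6.3 analysis model plus painDETECT, and 6.9 adds it to the rescue-medication model.

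**Working it through.** **Inputs from the documents.** N at most 200; dropout about 33% overall (SAP 5.2, Protocol 1.1 and 9.2). Allocation ratio, effect size, SD and efficacy criterion are redacted, so the sample size cannot be reproduced. The only available arithmetic is 0.33 × 200 = 66 missing and 200 − 66 = 134 observed at week 8. Everything below is an identity or rests on an assumed value.

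**1. Size of a departure.** Let p_L and p_P be the dropout proportions on LY3556050 and placebo, and δ the amount by which unseen NRS values are worse than MAR predicts.

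Move in the difference = p_L × δ_L − p_P × δ_P

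- LY3556050 only, δ = 1: 0.33 at 33% dropout; 0.23 and 0.43 if that arm's dropout is 23% or 43% (assumed range).
- Same δ in both arms: (p_L − p_P) × δ, which is 0 if dropout is equal.

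**2. Whether MAR imputation registers it.** A simulation under assumed values (effect −0.5 before any shift, SD 2, correlation 0.6, 33% dropout per arm, regression imputation, 200,000 per arm) gave:

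| δ in LY3556050 dropouts | True difference | MAR-imputed difference |
|---|---|---|
| 0 | −0.498 | −0.488 |
| 0.5 | −0.322 | −0.484 |
| 1.0 | −0.166 | −0.503 |
| 1.5 | −0.003 | −0.498 |

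The truth moves by about 0.33 × δ. The imputed estimate does not move, apart from simulation noise.

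**3. Shift that takes the point estimate to zero.** δ = effect / p_L, which is 1/0.33 = 3.03 times the effect at 33%.

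- Assumed effects 0.3, 0.6 and 1.0 at 33%: 0.91, 1.82 and 3.03 points.
- Assumed effect 0.6 at 23% and 43%: 2.61 and 1.40 points.
- A grid ending at 3 points reaches zero for effects up to 3 × p_L: 0.99 at 33%, 0.69 at 23%, 1.29 at 43%.

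**4. Where the shift is added.** Added after imputation, 1 point stays 1 point at week 8. Added at each weekly regression step, it carries forward. For someone leaving after week 4 under AR(1) correlation 0.8, it becomes 1 + 0.8 + 0.64 + 0.512 = 2.95 points; under exchangeable correlation 0.7 it becomes 1.41. The plan must therefore say which is meant.

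The post-imputation route was checked on 40 simulated trials of 200 imputations each (N = 200, 1:1, 33% dropout per arm, SD 2, AR(1) 0.8, effect −0.6). Shifts of 1 and 2 points moved the pooled estimate by 0.323 and 0.646, matching the realised p_L × δ. The shift is built in, so this confirms only that the identity survives the pooled analysis.

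**5. painDETECT.** SE ratio when a factor explaining R² of the variance is omitted = 1/√(1 − R²). At an assumed R² of 1%: 1/√0.99 = 1.005. At 5%: 1/√0.95 = 1.026. The loss is 0.5% to 2.6%.

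**The case against.** **The plan may already contain the analysis.** Section 6.3 supplements a master SAP that was not supplied, and the available text of 6.16 stops partway. A reader might infer that the sponsor plans no MNAR analysis at all. The documents do not support that. The revision history names no such analysis, but it lists only major Version 2 changes. This objection stands, and it makes the fix conditional.

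**The two analyses are not duplicates.** A reader might infer that the imputation and the MMRM must share any error and agree. That goes too far. The imputation adds age, gender and possibly the adverse-event indicator, so the two can diverge if those variables predict unseen outcomes. The narrower statement survives: neither responds to departures that these variables do not explain. The indicator can make MAR more plausible, but it does not test it.

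**Nothing shows that LY3556050 dropouts would do worse.** Correct. No passage establishes that, or unequal dropout between arms. Section 6.3 also promises only to examine missing data, not to test MNAR, and the trial is proof of concept. These points argue against calling the plan wrong. They do not remove the value of a test, given a third of endpoint values missing and an unverifiable assumption.

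**Section 6.2 may already bring in painDETECT.** Perhaps, but 6.3 gives explicit lists without it, so a programmer could follow either.

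**Conclusion.** The point holds in a limited form. Among the analyses that can be read, none tests departures from MAR beyond the observed variables, although about 66 of 200 week-8 values are expected to be missing. That no such analysis exists anywhere is not established.

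The size is 0.33 NRS points of treatment difference per point of one-sided departure, and zero for an equal departure in both arms with equal dropout. It rests on the planning figure of 33% applying to the LY3556050 arm. A tipping point for the interval, as opposed to the point estimate, is not given because the effect, its standard error and the efficacy criterion are not visible.

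This should be changed, but it does not undermine the primary analysis. The painDETECT omission is a matter of consistency with a small expected effect on precision. Two further items are clarifications only: the adverse-event indicator is labelled by discontinuation but defined by occurrence at any time, and 6.3 cites master SAP Version 4 where other sections cite Version 5.

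**What to change.** **1. Delta adjustment.** If the master SAP or the unseen part of 6.16 already specifies an MNAR analysis, cite it in 6.3 with its version. Otherwise prespecify the following in 6.3, before unblinding:

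- On the 200 planned imputations, add a shift to imputed post-discontinuation NRS values on LY3556050, after imputation and before the MMRM. A possible grid is 0 to 3 points in steps of 0.25.
- Repeat with the same shift on placebo.
- For VAS, use the same grid rescaled in proportion to the scale length.
- State whether shifted values are capped at the scale maximum.
- Report the estimate and interval at each shift, and the shift at which the point estimate reaches zero, or that it exceeds 3 points.

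The cost is SAP wording and one more table, which may look less favourable. No new imputations are needed.

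**2. painDETECT.** Add the two-level factor to the imputation and analysis models in 6.3, so that they match the stratified randomisation and the rule in 6.2. This costs one covariate.

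**3. Clarifications.** State whether the adverse-event indicator is used, align its label with its definition, and reconcile the Version 4 and Version 5 references.

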6.1. General Considerations

The estimand for the primary clinical question of interest has been described in the H0P-MC-CPMP SAP Version 5. The estimand is following a hypothetical strategy where the efficacy of LY3556050 is assessed under the assumption that the participants would have continued their initially randomized treatment condition even if they discontinued. Unless otherwise stated, all efficacy and safety analyses will be conducted for LY vs. Placebo, where all LY doses are combined.

Other general considerations for analyses are described in the H0P-MC-CPMP SAP Version 5.

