6.2. Adjustments for Covariates

The general adjustment strategy has been described in the H0P-MC-CPMP SAP Version 5.

Randomization into H0P-MC-BP03 is stratified by the presence of neuropathic pain as defined by the painDETECT score (Freynhagen et al. 2006).

The following stratification factor will be included in the models for the primary, secondary, and some exploratory outcomes.

Neuropathic pain	painDETECT score
Positive presence	≥19
Unclear or negative	<19

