6.7. Participant Characteristics

The summary of participant characteristics has been described in the H0P-MC-CPMP SAP Version 5.

ISA-specific considerations are described below.

- painDETECT ≥ 19 (ie, Positive for neuropathic pain)
- Roland Morris Disability Questionnaire (RMDQ) Total Score at baseline.

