6.10.2. Additional Analyses of the Primary Outcome

The overall mean treatment effect in change from baseline over the double blind treatment period will be reported for evaluating treatment effect for NRS, VAS, Roland Morris Disability Questionnaire (RMDQ), as well as other secondary continuous efficacy endpoints.

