6.10.3. Secondary Efficacy Analyses

The RMDQ is a simple, sensitive, and reliable method to measure disability in patients with back pain. The RMDQ consists of 24 statements relating to the person's perceptions of back pain and associated disability based on

- physical ability/activity
- sleep/rest
- psychosocial
- household management
- eating, and
- pain frequency.

Participants are asked if they feel the statement is descriptive of their circumstances on that day. The total score is obtained by counting the number of “Yes” responses, ranging from:

0 = no disability to 24 = maximal disability.

A Bayesian longitudinal mixed-effect model repeated measures (MMRM) analysis will be performed to evaluate the change from baseline to each postbaseline visit for the RMDQ total score. The model will utilize the constrained cell means model so that a common means is estimated at the baseline. More details on this approach are provided in the H0P-MC-CPMP SAP Version 5.

This table describes the information included in the model.

Categorical effects	
 The interaction of treatment and timepoint (constrained to estimate a common mean at baseline across treatments) Average baseline pain severity category (baseline NRS <7, baseline NRS \geq7) Presence of neuropathic pain (painDETECT \geq19, painDETECT <19) Pooled investigative site
Continuous covariates	
 None

Other Secondary Analysis

The proportion of participants in each treatment group meeting prespecified binary efficacy outcomes will be calculated for each post baseline time point and will be used to compare treatment groups. The prespecified binary efficacy outcomes include the proportion of participants:

- with a reduction \geq 30%, 50%, and 70% from baseline as measured by the RMDQ score, and
- with at least a 3.5 point reduction from baseline in the RMDQ score.

A Bayesian pseudo-likelihood-based categorical repeated measures regression model that includes all post baseline observations will be used to estimate the probability of achieving the response level in each treatment group and will be used to compare treatment groups.

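### SAP 6.3 does not name painDETECT, the randomisation stratification factor, in the imputation models of the NRS/VAS sensitivity analysis, and the covariate rule in SAP 6.2 does not clearly reach them

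*SAP*

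**What the plan says.** SAP 6.2 states that randomisation is stratified by neuropathic pain, defined by painDETECT score (≥19 against <19), and sets a rule: "The following stratification factor will be included in the models for the primary, secondary, and some exploratory outcomes".

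SAP 6.3 describes a sensitivity analysis of NRS and VAS that fits a constrained-cell-means MMRM to 200 imputed data sets. It gives three sets of variables:

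- Intermittent gaps: "The variable pooled investigative site, treatment, age, gender, baseline pain severity categories will be included for imputing non-monotone missingness".
- Monotone dropout: an indicator for the main adverse events leading to discontinuation "can be included as an additional variable for imputing monotone missingness".
- Analysis model: "The pooled investigative site, treatment and time interaction, baseline pain severity categories will be included as fixed effects".

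painDETECT appears in none of them. Elsewhere the SAP names it. The RMDQ model in 6.10.3 has the same effects as the 6.3 analysis model plus an entry that begins "Presence of neuropathic pain (painDETECT". SAP 6.9 adds painDETECT to the rescue-medication model and points back to 6.2.

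SAP 6.1 fixes the target: "The estimand is following a hypothetical strategy where the efficacy of LY3556050 is assessed under the assumption that the participants would have continued" their randomised treatment. SAP 5.2 plans up to 200 participants with about 33% dropout.

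**The concern.** Under a hypothetical estimand, imputed values stand for what participants would have reported had they stayed on treatment. About 200 × 0.33 = 66 week-8 values could be imputed, so the choice of imputation variables matters to this analysis.

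There are two readings, and each leaves something to tidy.

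1. If 6.2 does not reach 6.3, the sensitivity analysis drops a covariate that 6.2 requires for the primary outcome. A difference from the primary result would then mix a change in missing-data handling with a change in covariates.
2. If 6.2 reaches the 6.3 analysis model only, the imputation models lack a variable that the analysis model contains. They already go beyond the listed analysis model by including age and gender, yet lack the factor used to randomise.

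What is at stake is a small, avoidable shift in a sensitivity estimate whose purpose is to show how much missing data matter.

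**Working it through.** **How far the 6.2 rule reaches.** NRS is the primary outcome, and 6.10.2 lists NRS, VAS and RMDQ together, "as well as other secondary continuous efficacy endpoints". So 6.2 can fairly be read as adding painDETECT to the 6.3 analysis model by default. But 6.2 speaks of models for outcomes, and neither 6.2 nor 6.3 says that it extends to the imputation step.

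**Inputs.** From the documents: up to 200 participants and about 33% dropout. Effect size, SD, allocation ratio and efficacy criterion are redacted, so there is no figure of the plan to reproduce. Assumed: 35% painDETECT-positive; week-8 NRS higher in positives by b = 0.5, 0.8 or 1.2 points; SD 2.0; the same treatment effect (-0.6) in both strata; painDETECT unrelated to baseline NRS.

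**Hand calculation, with earlier visits giving no information.** If painDETECT is left out, dropouts in an arm are in effect imputed at the completers' mean. The shift in that arm's mean is

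shift = b × (share positive among completers − share positive among all).

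- Dropout 50% in positives and 25% in negatives: arm dropout 0.35 × 0.50 + 0.65 × 0.25 = 0.3375. Share positive among completers: 0.175 / (0.175 + 0.4875) = 0.264. Shift = b × (0.264 − 0.35) = −0.086b, or −0.04 (b = 0.5) to −0.10 (b = 1.2).
- Dropout 60% and 30%: share positive among completers 0.14 / (0.14 + 0.455) = 0.235. Shift = −0.115b, or −0.06 to −0.14.

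If both arms have the same pattern, both means shift equally and the difference does not move. If only one arm has it, the whole shift enters the difference. The allocation ratio does not enter this formula.

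**Simulation, with earlier visits used.** Sequential-regression imputation over weeks 2, 4, 6 and 8 on baseline NRS, baseline category, treatment and earlier visits; 2,000,000 participants, 1:1. Further assumptions: baseline SD 1.3, baseline to week-8 correlation 0.40, adjacent-visit correlation 0.80-0.85. Entries are the error in the LY3556050-placebo difference against the same data with nothing missing, for b = 0.5 / 0.8 / 1.2.

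| Dropout: LY positive, LY negative; placebo positive, placebo negative | painDETECT in neither model | Analysis model only | Both models |
|---|---|---|---|
| 50%, 25%; 50%, 25% | within 0.002 | within 0.002 | within 0.002 |
| 50%, 25%; 25%, 25% | −0.022 / −0.036 / −0.053 | −0.022 / −0.036 / −0.054 | 0.001 / 0.000 / 0.000 |
| 60%, 30%; 20%, 20% | −0.029 / −0.047 / −0.072 | −0.029 / −0.048 / −0.070 | 0.000 / −0.002 / 0.001 |
| 25%, 25%; 50%, 25% | +0.022 / +0.039 / +0.055 | +0.022 / +0.039 / +0.055 | −0.001 / 0.002 / 0.000 |
| 20%, 20%; 60%, 30% | +0.026 / +0.047 / +0.070 | +0.026 / +0.047 / +0.069 | −0.003 / 0.000 / −0.001 |

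Earlier visits roughly halve the hand-calculated shift. A negative error overstates the benefit and a positive one understates it. The second and third columns agree within 0.002, so the omission acts through the imputation. A repeat with 1,000,000 participants per scenario, at 1:1 and 2:1, gave 0.02 to 0.08 in size when dropout patterns differed by arm.

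**Other assumptions.** With 15% or 30% positive, b up to 1.0 and dropout related to painDETECT in opposite directions in the two arms, the error ran from about −0.01 to −0.12. In the most extreme 1:1 case it was −0.122 with painDETECT in neither model, −0.121 in the analysis model only, −0.002 in the imputation only and −0.001 in both.

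**Weekly data.** SAP 6.10.1 uses weekly NRS means. Eight weekly points reduced the shift by roughly 10-20% (for example −0.061 to −0.052, or 0.009 / 0.061 = 15%).

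**Precision.** At n = 200 with 1,800 replicates, the SD of the estimate was 0.282-0.322. Relative to painDETECT in both models, leaving it out gave a ratio of 0.993-1.009, so a main effect has no measurable cost.

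**The case against.** - **The 6.3 lists may not be closed.** They also do not name baseline NRS or earlier visits, which any sensible imputation of repeated measures would use and which the simulation supplied. An imputation regression for NRS might itself count as a model for the primary outcome. This stands as far as it goes: the text is ambiguous, and the documents do not prove that painDETECT would be left out.
- **The master SAP may settle it.** SAP 6.3 sends the general missing-data strategy to Version 4 and SAP 6.2 sends the adjustment strategy to Version 5. Neither was available, and SAP 5.3 on treatment assignment is redacted. A general rule cannot be excluded, but a programmer following the explicit lists in 6.3 would omit the factor.
- **Protocol 6.3 says this appendix adds no stratification factors.** That can mean none beyond the master protocol and the disease-state addendum, so it need not contradict SAP 6.2.
- **The simulation is not the 6.3 analysis.** It leaves out site, age, gender and the optional adverse-event indicator, which might absorb part of any arm-specific dropout. This stands, and the sizes are illustrative only.
- **A treatment effect that differs by stratum.** A reader might infer that the omission also causes bias when the effect differs by painDETECT, even with equal dropout patterns. The check does not support this: the bias is the same with painDETECT omitted or entered as a main effect. It is no argument for the fix.

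**Conclusion.** The point holds as a minor one. SAP 6.3 gives its own variable lists, the stratification factor is in none of them, and the rule in 6.2 does not clearly extend to imputation.

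With a common treatment effect, the difference between arms shifts only if painDETECT predicts outcome beyond earlier scores and painDETECT-related dropout differs between arms. The documents give no evidence for or against either condition. The illustrative size is 0.02 to 0.08 NRS points, or about 0.02 / 0.322 = 0.06 to 0.08 / 0.282 = 0.28 of a standard error. It is somewhat less with weekly data, zero when dropout patterns are equal across arms, and as much as 0.12 only under a deliberately extreme pattern. The positive share, its effect on NRS, the SD and the dropout patterns are all assumed.

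A reader might infer that the primary result is at risk. The documents do not support that: the primary analysis is the Bayesian MMRM, to which 6.2 assigns painDETECT, and the gap concerns one sensitivity analysis.

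**What to change.** In SAP 6.3, name painDETECT category (≥19 against <19) in the non-monotone imputation model, the monotone imputation model and the analysis model, in the analysis model in the same form as in the primary model. If it is left out on purpose, say why. A clause that only applies 6.2 to the analysis model would not be enough; the wording must name the imputation models.

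The cost is one sentence and one binary baseline variable, which SAP 6.7 already summarises ("ie, Positive for neuropathic pain"). It is a free improvement: impute and analyse by the groups the trial randomises by.

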6.10. Efficacy Analyses

6.10.1. Primary Outcome and Methodology

The analysis of the primary outcome has been described in the H0P-MC-CPMP SAP Version 5. The longitudinal model will include average NRS during the preliminary data entry period (PDEP, last 7 days prior to randomization at Visit 3) and within each nominal week of the double treatment period as a longitudinal outcome. As noted in Section 4.1, the endpoint for the primary analysis is defined as 8 weeks post initial treatment administration.

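### In the SAP 6.3 sensitivity model, a severity effect held constant over visits can cost precision for NRS, because the category is a cut of the baseline response

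*SAP*

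**What the plan says.** SAP 6.3 adds a multiple-imputation analysis, described "as a sensitivity analysis to assess change from baseline to postbaseline measure for visual analog scale (VAS) and NRS". After imputation, "The analysis model will utilize the constrained cell means MMRM so that a common mean is estimated at the baseline for each imputed dataset". Baseline is therefore part of the response vector, with one mean shared by the two arms. After pooled site and the interaction of treatment with time, the list of terms ends: "baseline pain severity categories will be included as fixed effects". The only interaction with time in that list is the one with treatment.

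SAP 6.3 does not define the severity categories. SAP 6.10.3 does, in the RMDQ model table: "Average baseline pain severity category (baseline NRS <7", the other level being 7 or more. SAP 6.10.1 confirms, for the primary model, that the NRS response consists of the average over the 7 days before randomization and the averages "within each nominal week of the double treatment period as a longitudinal outcome".

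**The concern.** In this type of model the precision gained from baseline comes through the estimated covariance between the baseline response and the later ones. For NRS the severity category is computed from that same baseline response. At baseline the two categories differ by construction. By week 8 the difference has been multiplied by the slope of week 8 on baseline, which is below 1 when there is regression to the mean. Read literally, 6.3 gives severity one coefficient for all time points. It cannot fit both gaps, so the misfit goes into the residual covariance and distorts the baseline adjustment.

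What is at stake is the width of the interval. This analysis is there to show what missing data do to the result. If its interval is wider than the primary one, part of the widening could come from the form of a covariate and be mistaken for an effect of missingness.

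**Working it through.** **Inputs.** From the documents: up to 200 participants and about 33% dropout (SAP 5.2); the model terms (SAP 6.3); the cut at 7 (SAP 6.10.3, assumed to apply in 6.3). Not given, so assumed: baseline NRS mean 6.5, baseline SD 1.0–2.0, post-baseline SD 1.5–2.4, baseline-to-week-8 correlation r of 0.2–0.6, allocation 1:1 or 2:1. The plan states no precision figure for this model, so there is none to reproduce.

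**Why a slope of 1 is the exception.** Take baseline Y0, week 8 Y8, severity s and slope γ = r·σ8/σ0. With one severity coefficient β at both times, s cancels from D = Y8 − Y0, and the model implies D = a + δ·treatment + θ(Y0 − βs) + error. If Y8 is linear in Y0, the true relation is D = a + δ·treatment + (γ − 1)Y0 + error. The two agree only if θβ = 0: either β = 0, which contradicts the baseline gap, or γ = 1.

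**Worked case: SDs 1.5 and 2.0, r = 0.4.**
- γ = 0.4 × 2.0/1.5 = 0.533.
- z = (7 − 6.5)/1.5 = 0.333. The share at or above 7 is p = 0.369, p(1 − p) = 0.233, and the normal density is φ(z) = 0.377.
- Write c = σ0·φ(z) = 0.566. The category gap at baseline is c/[p(1 − p)] = 0.566/0.233 = 2.43 points. At week 8 it is 0.533 × 2.43 = 1.30 points.
- Without a severity term, or with severity by visit, the week-8 variance given baseline is σ8²(1 − r²) = 4 × 0.84 = 3.36.
- With one coefficient b, the residual moments are V0 = σ0² − 2bc + b²p(1 − p), V8 = σ8² − 2bγc + b²p(1 − p) and C = rσ0σ8 − b(1 + γ)c + b²p(1 − p). Likelihood picks the b that minimises V0·V8 − C², here b = 2.30. Then V0 = 2.25 − 2.60 + 1.23 = 0.88, V8 = 4 − 1.39 + 1.23 = 3.84 and C = 1.20 − 2.00 + 1.23 = 0.44 (components rounded). The conditional variance is V8 − C²/V0 = 3.63.
- Variance ratio: 3.63/3.36 = 1.08. At N = 200 and 1:1 the SEs are √(4 × 3.36/200) = 0.259 and √(4 × 3.63/200) = 0.269.

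Simulation with more time points and the same SDs and r gave model SEs of 0.2568 (no term), 0.2669 (constant) and 0.2568 (by visit), and (0.2669/0.2568)² = 1.08.

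**Range for NRS** (simulation, N = 200, 1:1, complete data). Variance ratio of the constant term to no term, with the slope in brackets:

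| Baseline SD / week-8 SD | r = 0.2 | r = 0.4 | r = 0.6 |
|---|---|---|---|
| 1.2 / 2.2 | 1.06 (0.37) | 1.02 (0.73) | 1.00 (1.10) |
| 1.5 / 2.0 | 1.15 (0.27) | 1.08 (0.53) | 1.02 (0.80) |
| 1.5 / 1.5 | 1.23 (0.20) | 1.18 (0.40) | 1.12 (0.60) |
| 2.0 / 2.0 | 1.24 (0.20) | 1.18 (0.40) | 1.12 (0.60) |

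The slope alone does not fix the loss: at 0.60 with equal SDs it is 12%, above the 2–8% seen with SDs of 1.5 and 2.0. At a slope of 1.44 a small loss returns (about 1.03–1.04). The mean error of the treatment contrast was at most 0.02 points.

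**With 33% monotone dropout, multiple imputation and Rubin's rules** (2:1, 10 imputations where the plan has 200, 200 runs):

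| SDs, r | No term | Constant | By visit | Variance ratio, constant to none |
|---|---|---|---|---|
| 1.5 / 2.0, 0.4 | 0.3134 | 0.3220 | 0.3130 | 1.06 |
| 1.5 / 1.5, 0.3 | 0.2401 | 0.2575 | 0.2402 | 1.15 |
| 1.2 / 2.2, 0.5 | 0.3259 | 0.3264 | 0.3260 | 1.00 |

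**VAS.** Here the category comes from another scale. If it adds nothing beyond baseline VAS, the ratio is 1.02–1.08. If it carries information of its own, the ratio is 0.89–1.07, so the constant term can beat leaving it out.

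**The case against.** A reader might infer that the listed term always makes the estimate noisier than leaving it out. It does not: near a slope of 1 there is no loss, and a narrow baseline with a wide week 8 brings the slope there. The general entry criteria, which shape the baseline spread, are in the master protocol and the disease-state addendum, which are not supplied.

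A reader might extend the point to VAS in the same form. The mechanism needs the category to be a function of the response, which holds only for NRS.

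A reader might also see lost trial power or a flaw in the primary analysis. SAP 6.10.1 places the primary model in the master SAP, which is not available, and the visible text ties no success criterion to the 6.3 model. Nor is a loss claimed for the RMDQ model in 6.10.3, where the category again comes from another scale. All of this stands and limits the point.

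The list in 6.3 may also be shorthand. It omits painDETECT, which SAP 6.2 puts in the primary, secondary and some exploratory models. The fitted model may therefore already contain severity by visit. That possibility stands, and one sentence would settle it.

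Finally, if the primary model uses a constant term, changing only the sensitivity model would mix a change of model with the missing-data comparison. That is a reason to state the form openly, but it does not remove the loss.

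**Conclusion.** As written, the 6.3 model holds the severity effect constant while baseline is a response. For NRS this can make the week-8 treatment estimate noisier than omitting the term. The variance cost runs from about 0% with the slope near 1, through 2–8% at slopes of 0.53–0.80 with SDs of 1.5 and 2.0, to about 24% at low slopes with equal SDs. The figures rest on assumed SDs, correlations and allocation, and on the cut at 7 carrying over from 6.10.3. For VAS the direction is open. There was no material bias. This is a minor precision point about a sensitivity analysis.

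**What to change.** In SAP 6.3, replace the severity term with severity category by visit for both NRS and VAS, and state the cut there. For NRS, dropping the term is equivalent in precision. For VAS, dropping it could discard useful information, so the by-visit form is the better single choice. If that form is already intended, one clarifying sentence closes the point. If it differs from the primary model in the master SAP, say so where the two results are compared.

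The cost is one SAP sentence and one model term: a severity coefficient per time point in place of a single one, so a few degrees of freedom. In the NRS simulations the by-visit form had essentially the same SE as the model without severity.
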